7.2 Food insulin index (FII) and insulin response

To assess the FII of the common bean product *in vivo*, 10 healthy volunteers will be recruited from Jomo Kenyatta University of Agriculture and Technology. Insulin response associated with consumption of the common bean product will be assessed in 10 T2DM patients in Makueni County. Participants will be fed with iso-caloric (240 kilocalorie) portions of the test food and reference food.

Inclusion and exclusion criteria for the FII and insulin response used will be as cited in GI study (see section 7.1).

The FII of the food will be measured over a 120 min period starting at the ingestion of the common bean product. The test food and reference food will be assessed in each subject on separate days with a 1 week period between each study day.

The FII value of the common bean product will be calculated as follows: = [iAUC of the common bean product/individual subject's average iAUC of reference food]*100. The overall FII will then be obtained as: The mean FII value for the 10 participants.

³ The standard was issued under licence to [name] (co-principal investigator)

Insulin response associated with consumption of the common bean product will be assessed in 10 T2DM patients in Makueni County.

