Insulin release can be triggered by other food components such as proteins and fats. The food insulin index (FII) allows for testing of foods with no or low carbohydrate content. It shows the observed (plasma) insulinemic response to consumption of a particular food compared to an isocaloric portion of the reference food over a 2 hour period. It is obtained as: $\frac{\text{iAUC for 1000kJ test food}}{\text{iAUC for 1000kJ reference food}} * 100$. FII has previously been reported to have potential of reducing postprandial hyperinsulinaemia in T2DM management [47].

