7. STUDY DESIGN AND SAMPLING STRATEGY

7.1 Glyceimic index (GI) and glyceimic response study

The GI evaluates the blood-raising ability of equi-carbohydrate portions of different single foods or mixed meals. To assess the GI of the common bean product *in vivo*, 10 healthy volunteers will be recruited. The selection of the number of participants, and the inclusion and exclusion criteria is based on the ISO_26642_2010 standard [53].

The 10 healthy volunteers will be recruited from Jomo Kenyatta University of Agriculture and Technology (JKUAT) and handled at the JKUAT University Hospital.

Inclusion criteria:

- Male or female 18-69 years
- No known food allergies or intolerances
- No prescription medication² (excluding oral contraceptives) known to affect glucose intolerance (e.g. steroids, protease inhibitors, antipsychotics e.t.c.)

Exclusion criteria

- Known history of diabetes mellitus or use of anti-hyperglycaemic medication or insulin
- Alcohol or tobacco use in the evening preceding the test
- Vigorous exercise on the morning of the test
- Undergone major medical/surgical event needing hospitalization within the preceding 3 months
- Presence of disease or drug influencing digestion and absorption of medicine

Glycemic response associated with consumption of the common bean product will be assessed in 10 T2DM patients in Makueni County. The participants will be recruited from the **Makueni Level-5 and Mbooni sub-county hospitals** which run a diabetes outpatient clinic.

Inclusion criteria:

- Male or female aged 18-69 years
- Previously diagnosed with type 2 diabetes
- Consenting to participate

Exclusion criteria:

- Use of prescription medication
- History of eating disorders and irregular eating habits
- Use of tobacco or alcohol
- Females experiencing menstrual period or adverse premenstrual symptoms

For the reference food, we will use either anhydrous glucose powder, 50g or dextrose (glucose monohydrate), 55g. The reference food will be dissolved in 250ml of water and refrigerated for use within 72 hours after preparation. Participants will be fed with an equi-carbohydrate portion of the common bean product to the reference food.

² Stable doses of oral contraceptives, acetylsalicylic acid, thyroxin, vitamins and mineral supplements or drugs to treat hypertension or osteoporosis are acceptable

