7.4 GI and FII study procedures

Researchers will obtain signed consent from the participants before testing. For the GI and FII study, the common bean product will be served with a standard 250 ml portion of water. Participants will first receive the reference food and then the test food on separate mornings after a 10-12h overnight fast. The conditions and testing times during the test days will be as similar as possible. Participants will be asked beforehand to maintain their usual diet; avoid alcohol; and not engage in unusual or excessive physical activity on the day preceding the test. For the night preceding the test day, participants will be asked to eat a standard evening meal that allows for the 10h fasting period prior to the study and refrain from eating and/or drinking (except for water).

On the test day, arrival time to the hospital will be 0700h. The researchers will assist participants in filling out a 24 hour dietary recall. Anthropometric measurements (weight, height, waist and hip circumferences); blood pressure; and body composition using bioelectrical impedance analysis (BIA) will be assessed. The subsequent tests will be conducted while the participants are in a rested position. A catheter will be introduced in the cubital vein to obtain venous blood by a phlebotomist. Two blood samples will be obtained within a five minutes interval in the fasting state, and their average taken as the baseline blood glucose concentration (time -5 and time 0). Participants will then be given the test food and 250ml water all presented in standard bowls and/or glasses. Participants will be asked to eat the whole portion in 12 to 15 minutes, at an even pace. Time taken to eat the entire portion will then be recorded. Participants will remain seated and will be allowed to read or use their phones. They will however not be allowed to sleep or eat or drink until the end of the 2h of study period.

[figure not shown]
Postprandial blood samples will be collected after the feeding at six time-points, 15, 30, 45, 60, 90 and 120 min. For each time point, ~2 ml of blood will be obtained. Whole-blood samples will be labelled using codes allocated to each participant for proper identification. Blood glucose content will be measured in either whole blood or plasma samples. Centrifugation will be done within 30 minutes of blood collection using portable centrifuges carried to the field. Blood plasma or serum

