7.5 Appetite scores using Visual Analog Scales (VAS)

Appetite scores will be used to assess the satiety power of the test (common bean) product among T2DM participants. The appetite score will be taken on one study day, that is, after consumption of the bean product. Subjective measures of appetite will be taken prior to, and at predetermined time intervals after consumption of the test meal. Appetite score refers to the average between hunger, desire to eat, prospective consumption and a 100-fullness score. The appetite score will be assessed at before and after consumption of test product at time points 0, 15, 30, 45, 60, 90 and 120 minutes. Participants will be given a short questionnaire to assess satiety.

A single vertical mark best expressing the participants' response will be made on an anchored 100 mm VAS scale. The anchor on the left and right will express the most positive and the most negative rating respectively (see Appendix 7). The response will be quantified by measuring the distance between the left anchor and the marking made. The questionnaires will be made as a small brochure booklet showing one question at a time [54][55]. Participants will be asked to remain silent while filling out their VAS. Between evaluations, they will be allowed to read or use their phones. The participants will not be allowed to discuss with each other or refer to previous ratings when filling out the VAS.

Blood draw + Appetite scores

Figure 3: Summary of protocol for the assessment of postprandial glycemic, insulinemic and satiety responses

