8. DATA COLLECTION

8.1 Data collection processes

Glycemic index and glycemic response (*Appendix 2*)

- a. Equi-carbohydrate (50g or 25g) portions of the common bean product
- b. 24-hour of dietary recall
- c. Anthropometry: weight, height, waist & hip circumference
- d. Body composition: BIA
- e. Biochemical samples: Blood

Food insulin index (FII) and insulin response (*Appendix 2*)

- a. Iso-caloric (240kJ) portions of the common bean product
- b. 24-hour of dietary recall
- c. Anthropometry: weight, height, waist & hip circumference
- d. Body composition: BIA
- e. Biochemical samples: Blood

Appetite scores (*Appendix 3*)

- a. Visual analog scales
- b. Timers

BIA will be assessed with the Bodystat 500 (Bodystat, UK). Raw data on impedance, resistance, reactance and phase angle will be added to already validated equations to calculate fat free mass, body fat and hydration [56].

For blood draw, handling and processing; phlebotomists from the Kenya Medical and Research Institute (KEMRI) will be engaged. A catheter will be placed in the cubital vein. Blood samples will be collected at seven time-points; 0, 15, 30, 45, 60, 90 and 120 minutes. For each bleeding moment ~2 ml of blood will be drawn from the participant. Plain tubes will be used for blood collection. After collection, whole-blood samples will be labelled with codes with participant

codes and separated based on time-collection point. A drop of blood will then be obtained for determination of haemoglobin concentration using the Hemocue 301 portable device. The tubes will then be placed immediately into insulated coolers containing ice/cold packs at around 4°C awaiting centrifuging. Centrifuging will be within 30 minutes of sample collection. After centrifuging, serum will be separated and divided in aliquots. Cryovials containing the aliquots will be labelled (with participant code and test to be run), wrapped with aluminum foil (to reduce chances of light degradation) and secured together with rubber bands. They will then be put in a portable freezer. At the end of sample collection and separation, the aliquots will be dropped into a liquid nitrogen tank awaiting transportation to analytical laboratories (LANCET), for further analysis. Necessary precautions will be taken to ensure a dust and light free environment during the blood sample collection and handling.

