Anthropometric and body composition measurements

| | | | |
|--|----|-----------|----------------|
| Tefal Weight scale | 4 | 4,000/pc | 16,000 |
| Seca portable/wall mounted stadiometer with movable head piece, or measuring rod | 4 | 7,000/pc | 28,000 |
| Waist circumference tape | 10 | 1000/pc | 10,000 |
| Bodystat 500 | 1 | 80,000/32 | 80,000 |
| Subtotal | | | 134,000 |

Laboratory Blood Specimen Analysis Costs

| | | | |
|---|-----|-------|------------------|
| Blood glucose (30 fasting, 180 random) | 210 | 649 | 136,290 |
| Plasma insulin (fasting) | 30 | 3,849 | 115,470 |
| Plasma insulin (non-fasting) | 180 | 4,149 | 746,820 |
| C-peptide (fasting/non-fasting) | 20 | 2,949 | 58,980 |
| HbA1C | 20 | 2,949 | 58,980 |
| Lipid profile (Cholestrol, HDL,LDL,Trig+Ratio calculations) | 20 | 2,949 | 58,980 |
| Subtotal | | | 1,175,520 |
| TOTAL | | | 1,643,775 |
| Miscellaneous (flat rate) | | | 10,000 |
| GRAND TOTAL | | | 1,653,775 |

Funding: VLIR-UoS

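### GI and FII need differently matched bean/reference pairs, but the plan appears to provide only one pair for both

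*Combined protocol and SAP*

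**What the plan says.** Two matching rules are given.

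- **GI, section 7.1:** "Participants will be fed with an equi-carbohydrate portion of the common bean product to the reference food". The reference is 50 g anhydrous glucose or 55 g dextrose. No other reference amount appears among the study procedures.
- **FII, section 7.2:** "Participants will be fed with iso-caloric (240 kilocalorie) portions of the test food and reference food". Section 3.5 defines the FII as the insulin response to a food "compared to an isocaloric portion of the reference food over a 2 hour period", and its formula uses 1000 kJ of each food.

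Section 8.1 lists the portions again: "Equi-carbohydrate (50g or 25g) portions of the common bean product" for GI and "Iso-caloric (240kJ) portions of the common bean product" for FII.

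The visits are described jointly. Section 7.4 covers GI and FII under one heading: "Participants will first receive the reference food and then the test food on separate mornings after a 10-12h overnight fast". It then lists glucose and insulin among the analytes for the blood samples. Section 7.5, on the patients with type 2 diabetes (T2DM), says: "The appetite score will be taken on one study day, that is, after consumption of the bean product". The laboratory lines in section 12.3 read "Blood glucose (30 fasting, 180 random" for glucose, and give the same 30 and 180 for fasting and non-fasting insulin.

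**The concern.** GI and FII answer different questions because they hold different things equal: carbohydrate for one, energy for the other. Beans supply energy from protein as well as carbohydrate (section 3.2 gives 14% to 33% protein, depending on the variant). A portion matched to glucose on carbohydrate therefore carries more energy than the glucose, and a portion matched on energy carries less carbohydrate.

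If a single bean/reference pair supplies both indices, one of them is reported from a comparison that its own definition excludes. Nothing in sections 9.2 or 9.3 adjusts for this, and it cannot be repaired once the portions have been eaten. Glucose, insulin and appetite responses are the whole objective (section 4.1). The portion to which the appetite score refers is also left open.

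**Working it through.** **1. Reproduce the budget count.** Section 8.1 has seven blood samples per session, one fasting and six after the meal.

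- Glucose: 30 + 180 = 210 assays; 210 / 7 = 30 sessions.
- Insulin: 30 + 180 = 210 assays; 210 / 7 = 30 sessions.
- One layout gives exactly this: 10 healthy × (1 reference + 1 bean) + 10 T2DM × 1 bean = 30 sessions.
- Lunches: 30 over 3 days, one per session in that layout. Tubes: 2 packs of 100 = 200.

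**2. What separate pairs would need.**

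| Layout | Sessions | Samples (× 7) |
|---|---|---|
| Healthy: two references, two beans; T2DM: two beans | 4 × 10 + 2 × 10 = 60 | 420 |
| All 20 take two references and two beans | 4 × 20 = 80 | 560 |
| As above, each reference given twice (section 11) | 6 × 20 = 120 | 840 |

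Even two bean sessions for 20 people make 40 sessions, against 30 lunches.

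**3. Can one pair meet both rules?** Let the reference be G g of glucose, and let the bean portion hold C g available carbohydrate plus N kcal from other sources. At an assumed 4 kcal/g:

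- equal carbohydrate: C = G
- equal energy: 4C + N = 4G

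Both hold only if N = 0, that is, if all the product's energy is available carbohydrate.

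**4. The reference amounts differ.** 50 g × 4 = 200 kcal, while 240 / 4 = 60 g. At an assumed 3.74 kcal/g the figures are 187 kcal and 64 g. Either way, the stated 50 g drink is not the 240 kcal drink.

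**5. Size of the load mismatch.** Product composition is not given, so two assumed sets are shown. With a 50 g-carbohydrate portion, bean energy is E = 200 + 4 × protein (g) + 9 × fat (g). With a 240 kcal portion, bean carbohydrate is 50 × 240 / E.

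- *Set A:* 0.2 to 0.6 g protein per g carbohydrate, fat ignored. E = 200 × 1.2 to 200 × 1.6 = 240 to 320 kcal, a ratio to 200 of 1.2 to 1.6. Carbohydrate in 240 kcal = 50 to 37.5 g, a ratio to 60 g of 0.83 to 0.63.
- *Set B:* bean solids with 35% to 45% available carbohydrate, 14% to 33% protein and 2% fat.
  - Low end: 200 + 4 × 50 × 14/45 + 9 × 50 × 2/45 = 200 + 62 + 20 = 282 kcal.
  - High end: 200 + 4 × 50 × 33/35 + 9 × 50 × 2/35 = 200 + 189 + 26 = 414 kcal (rounded total).
  - Energy ratio 1.41 to 2.07. Carbohydrate in 240 kcal = 42.5 to 29.0 g, a ratio to 60 g of 0.71 to 0.48.

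Together: 1.2 to 2.1 times the reference energy, or 0.48 to 0.83 of the reference carbohydrate. Halving both foods to the 25 g option in section 8.1 leaves the energy ratio unchanged.

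**6. The FII portion has inconsistent units.** 240 kcal × 4.184 = 1004 kJ, which agrees with the 1000 kJ in section 3.5. The 240 kJ in section 8.1 is 240 / 4.184 = 57 kcal, about a quarter of it.

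**The case against.** No sentence says that one bean session serves both indices. Sections 7.1 and 7.2 each give their own recruitment, portion rule, test and reference days a week apart, and formula; section 8.1 lists two data-collection processes. Read literally, these are two sub-studies and no portion is wrong.

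The evidence for one session is also indirect:

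- Section 7.4 may simply state procedures common to both sub-studies. Its analyte list is not a rule for every sample, since it includes the lipid profile and only 20 lipid profiles are budgeted.
- Section 7.5 fixes the day of appetite scoring, and only for the T2DM patients.
- Appendix 2 is a dated form that could be reused at each session.
- 210 + 210 assays would also fit 30 glucose-only and 30 insulin-only sessions.
- The budget lists 80 needles, 80 IV tubes and 80 swabs, which fits 20 people × 4 sessions.
- Thirty sessions cannot supply one reference and one bean day for all 20 people (40), nor the repeated reference in section 11, so the budget is an imperfect guide.
- The visit figures and participant information sheets could not be read here and may state the visits.

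All of this stands as a reason not to treat the single session as fact. It does not remove the point. Thirty glucose-only plus thirty insulin-only sessions would need 60 lunches and 420 tubes, against 30 and about 200. In the readable text, no section sets out the total sessions per person or converts 240 kcal into a reference amount. Even if two sub-studies are intended, the plan needs to say so.

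**Conclusion.** The two matching rules conflict for any single bean/reference pair, and this needs no assumption about composition beyond the product having some energy other than available carbohydrate. That one pair is planned is an inference, but the better-supported one. If it is run, either the FII is not isoenergetic or the GI is not equi-carbohydrate.

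Three stronger readings are tempting and are not supported:

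- *At least one index is certain to come from the wrong portion.* This holds only if one pair is run, which the documents do not state.
- *No single bean portion can satisfy both rules.* A portion that happened to hold 50 g carbohydrate and 240 kcal (0.2 g protein per g carbohydrate, fat ignored) would fit section 7.1 against 50 g glucose and section 7.2 against about 60 g. The fault would then lie in the shared reference drink, so the conflict belongs to the pair.
- *The load ratios are percentage errors in the indices, or the GI will be biased in the product's favour.* That needs responses proportional to load, and protein and fat energy as insulinogenic as glucose energy; no document says so. Sections 7.1 and 8.1 also tie the GI to the equi-carbohydrate portion, and nothing indicates that it would be taken from the 240 kcal one.

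The size of any error therefore cannot be fixed from the documents. The ranges 1.2 to 2.1 (energy) and 0.48 to 0.83 (carbohydrate) describe mismatched loads under assumed composition only.

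**What to change.** Before the first feeding session, reconcile sections 3.5, 7.1, 7.2, 7.4, 7.5, 8.1 and 12.3, including the 240 kcal, 240 kJ and 1000 kJ entries. Add a short table giving, for each group:

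- the number of bean and reference sessions per participant;
- the matching rule and the reference amount for each session;
- the analytes measured at each session;
- the bean session on which appetite is scored.

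State in section 9.2 that GI is computed only from an equi-carbohydrate pair and FII only from an isoenergetic pair.

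If one pair is run, keep the index whose matching rule it meets. Report the other measure as a descriptive response ratio (bean iAUC over reference iAUC) under a different name. This costs wording only, with no extra visits or assays, but one named index is lost.

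If both indices are to be kept, schedule separate pairs. On the counts above this takes at least 60 sessions rather than 30, with more if T2DM patients take the references or references are duplicated. Lunches, tubes and any added assays would have to be re-budgeted to match.

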7.4 GI and FII study procedures

Researchers will obtain signed consent from the participants before testing. For the GI and FII study, the common bean product will be served with a standard 250 ml portion of water. Participants will first receive the reference food and then the test food on separate mornings after a 10-12h overnight fast. The conditions and testing times during the test days will be as similar as possible. Participants will be asked beforehand to maintain their usual diet; avoid alcohol; and not engage in unusual or excessive physical activity on the day preceding the test. For the night preceding the test day, participants will be asked to eat a standard evening meal that allows for the 10h fasting period prior to the study and refrain from eating and/or drinking (except for water).

On the test day, arrival time to the hospital will be 0700h. The researchers will assist participants in filling out a 24 hour dietary recall. Anthropometric measurements (weight, height, waist and hip circumferences); blood pressure; and body composition using bioelectrical impedance analysis (BIA) will be assessed. The subsequent tests will be conducted while the participants are in a rested position. A catheter will be introduced in the cubital vein to obtain venous blood by a phlebotomist. Two blood samples will be obtained within a five minutes interval in the fasting state, and their average taken as the baseline blood glucose concentration (time -5 and time 0). Participants will then be given the test food and 250ml water all presented in standard bowls and/or glasses. Participants will be asked to eat the whole portion in 12 to 15 minutes, at an even pace. Time taken to eat the entire portion will then be recorded. Participants will remain seated and will be allowed to read or use their phones. They will however not be allowed to sleep or eat or drink until the end of the 2h of study period.

[figure not shown]
Postprandial blood samples will be collected after the feeding at six time-points, 15, 30, 45, 60, 90 and 120 min. For each time point, ~2 ml of blood will be obtained. Whole-blood samples will be labelled using codes allocated to each participant for proper identification. Blood glucose content will be measured in either whole blood or plasma samples. Centrifugation will be done within 30 minutes of blood collection using portable centrifuges carried to the field. Blood plasma or serum

will then be pipetted into aliquots in cryovials, labelled, wrapped with aluminium foil and stored in liquid nitrogen awaiting transportation to LANCET laboratories for analysis. The blood samples will be analysed for blood glucose, insulin, lipid profile and C-reactive protein.

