The GI of the food will be measured over a 120 min period starting at the ingestion of the common bean product. The test food and reference food will be assessed in each subject on separate days with a 1 week period between each study day.

The GI value of the common bean product will be calculated as follows: = [iAUC of the common bean product/individual subject's average iAUC of reference food]*100. The overall GI will then be obtained as: The mean GI value for the 10 participants.

The test conditions, sample size and methodology are as adopted from the international standard ISO 26642:20110(E)³ [53].

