9.2 Glycemic and insulineric tests

Allowable mean within-subject co-efficient of variance (CV) for the reference food is $\leq 30\%$. The laboratory's inter-assay analytical variation on standard solutions should be $< 3.6\%$. The laboratory's minute-to-minute analytical variation in human subjects for 20 or more duplicate measurements of fasting glucose should generally be $< 5\%$. Glycemic and insulineric responses will be obtained from the iAUC (incremental area under the curve). iAUC is calculated by applying the trapezoid rule (sums of the areas of the triangles and trapezoids) [53]. iAUC is reported in millimole minutes per litre. Below is an example to how the iAUC and GI will be arrived at:

Table 2: Sample blood glucose responses to the ingestion of a 50g carbohydrate portion

| Food sample | Time of sampling, min | | | | | | | iAUC |
|----------------------------|-----------------------|-----|-----|-----|-----|-----|-----|------|
| | 0 | 15 | 40 | 45 | 60 | 90 | 120 | |
| Reference food replicate 1 | 4.3 | 6.3 | 7.9 | 5.3 | 4.1 | 4.6 | 4.9 | 114 |
| Reference food replicate 2 | 4.0 | 6.0 | 6.7 | 5.5 | 5.3 | 5.0 | 4.2 | 155 |
| Test food | 4.0 | 5.0 | 5.8 | 5.4 | 4.8 | 4.2 | 4.4 | 93 |

The iAUC for the Reference food replicate 1 = sums of the areas of the triangles and trapezoids A to F obtained after plotting the blood glucose responses at the different time intervals on a graph (Fig. 4).

Key

- c_{Glc} blood glucose
- r' horizontal side of triangle D
- r'' horizontal side of triangle E

Figure 4: Graph of blood glucose responses to the ingestion of a 50g carbohydrate portion over a 2h period

Calculation for GI

- Mean iAUC for the reference food= (iAUC reference food replicate 1+ iAUC reference food replicate 2)/ 2= 135±29 mmol min/l
- The CoV is thus $29/135*100 = 22\%$ (Test condition: CV for the reference food for the group should be $\leq 30\%$).
- iAUC for test food is 93 mmol min/l. For this subject, GI of the test food is thus $93/135*100 = 69\%$.

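### Everyone receives the reference food before the bean product, so GI and FII cannot be separated from a visit effect; a balanced order is a cheap remedy

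*Combined protocol and SAP*

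**What the plan says.** Section 7.4, which governs both indices, sets one order for all: "Participants will first receive the reference food and then the test food on separate mornings after a 10-12h overnight fast". Sections 7.1 and 7.2 put a week between study days. Section 7.4 asks for an overnight fast, a standard evening meal and test conditions and times that are as alike as possible. No section randomises or balances the order.

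Sections 7.1 and 7.2 define GI and FII for each person as the bean-product iAUC over that person's average reference iAUC, times 100, and then average over the 10 participants. Neither they nor section 9 includes a term for visit or order.

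The number of reference sessions is not consistent:

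- The worked example in section 9.2 uses two: "Mean iAUC for the reference food= (iAUC reference food replicate 1+ iAUC reference food replicate 2)/ 2". Section 11 also says the reference is tested twice, and the averaged denominator in section 7.1 fits that.
- Section 7.4 gives no number.
- The budget (section 12.3) prices 30 fasting and 180 later glucose assays. At six postprandial samples per session this is 180/6 = 30 sessions, which fits 10 volunteers × 2 plus 10 patients × 1. Two reference sessions would need 10 × 3 + 10 × 1 = 40.

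**The concern.** If responses differ systematically between visits (for example through familiarity with the procedure, or something peculiar to one study day), a fixed order places that difference on one food for every participant. All 10 ratios then move the same way. Averaging does not remove such a shift, and the reported SEM does not reflect it.

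GI and FII are the product-profiling results, which section 1 says are meant to inform dietary management. The one-week gap, fast and standard meal narrow visit differences but do not separate them from food. Section 11 acknowledges day-to-day variation, but not that day and food move together.

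The budget hints at group days without stating them: 30 lunches over 3 days is 10 a day. The staff lines are costed for 4 days, which at 10 people a day would be 40 sessions. If sessions are group days, any event on one day affects a single food for everyone.

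**Working it through.** **The plan's own example (section 9.2).** The trapezoid rule above fasting, with the third sample at 30 minutes as in section 7.4, gives iAUCs of 113.95, 155.25 and 93.0. The reference mean is 134.6, SD 29.2, CV 21.7% and GI 93.0/134.6 = 69.1%. The printed 135 ± 29, 22% and 69% are reproduced. (The table's column heading of 40 minutes does not reproduce them; it gives a GI of 65.8.)

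**Identifiability.** Model: log iAUC with subject, food and one term per visit, 10 people.

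| Order | Columns | Rank | Food estimable |
|---|---|---|---|
| Fixed, one reference session | 12 | 11 | no |
| Fixed, two reference sessions | 13 | 12 | no |
| Balanced 5/5 | 12 | 12 | yes |
| Balanced over three visits | 13 | 13 | yes |

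With two reference sessions, a strictly linear drift could be removed by extrapolating from the replicates. The variance of the food effect would then be 0.60σ² instead of 0.15σ² (σ = within-person SD), and the planned ratio does not do this.

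**Bias of the planned mean ratio.** The shifts are assumptions. Let iAUC be multiplied by 1+p at the first visit or by 1+q at the final visit.

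- First visit, one reference: factor 1/(1+p) = 0.909 or 1.111 at p = +0.10 or -0.10.
- First visit, two references: 1/(1+p/2) = 0.952 or 1.053.
- Final visit, one or two references: 1+q = 1.10 or 0.90. A second reference session gives no protection.

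Applied to a GI of 69:

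| Shift | One reference | Two references |
|---|---|---|
| First visit +10% / -10% | 63 / 77 | 66 / 73 |
| Final visit +10% / -10% | 76 / 62 | 76 / 62 |

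If the change instead accumulates at +10% or -10% of the first-visit level per visit over three visits, the factor is (1+2d)/(1+d/2) with d = +0.10 or -0.10, and a GI of 69.1 becomes 79.0 or 58.2.

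**Could the replicates reveal a first-visit shift?** The SE of the replicate contrast in 10 people is √2 × CV/√10. This is 9.8% at a CV of 22% (the example) and 13.4% at the 30% ceiling in section 9.2. Power to detect a 10% shift (noncentral t, 9 df, two-sided 5%) is about 15% and 10%.

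**Scale.** The within-person SE of mean GI is CV × √((1+1/m)/10), with m reference sessions. At 22% this is 9.8% (m = 1) or 8.5% (m = 2). A single-visit shift of 10% is therefore worth at most about 1.2 SE: 11.1/9.8 = 1.1 and 10/8.5 = 1.2.

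**After balancing.**

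- 5/5: 0.5(1+p) + 0.5/(1+p) = 1.0045 or 1.0056, that is +0.5% or +0.6%.
- 3/4/3: 0.3(1+p) + 0.7/(1+p/2) = 0.9967 or 1.0068, that is -0.3% or +0.7%. The final-visit case is the same, because the bean product is also third in 3 of 10.

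**Precision with a visit term.** The SE of food in units of σ stays at 0.447 (5/5) and moves from 0.387 to 0.389 (3/4/3). At 22% that is 9.8% unchanged, and 8.5% to 8.6%. With the lost degrees of freedom, 95% intervals widen by about 2% and 1%.

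**The case against.** The strongest reply is that no harm is shown. GI and FII are descriptive means in 10 people, no test or threshold in the plan depends on them, and no visit effect is documented. Two reference sessions is the only number the text states. On that reading a 10% first-visit shift moves GI by about 5%, roughly 0.6 SE, and the larger figures need a single reference session or an effect that appears late. All this stands, and it keeps the point at the level of a cheap improvement. It does not remove the confounding: under the fixed order the data could not show that a final-visit effect is absent.

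Section 7.1 says the "test conditions, sample size and methodology are as adopted from the international standard". What that ISO standard says on order is not in the documents, so it cannot be judged here whether the change would affect declared conformity. The sponsor holds the standard and should check.

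The budget conflicts with itself (lunches for 3 days, staff for 4), so the group-day reading is only suggestive. Nothing in the calculations depends on it. The 22% CV comes from one illustrative subject, which is why the 30% ceiling is shown beside it for the replicate contrast.

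Finally, serving the bean product on two or three days instead of one could add batch variation. The documents give no batch or shelf-life information for it, so this cost is real but cannot be sized.

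**Conclusion.** The concern holds. With one reference session, food and visit are fully confounded in GI and FII. With two, a final-visit effect remains confounded, and a first-visit shift would rarely be detected and is not corrected. An assumed 10% shift at one visit moves the indices by about 5% to 11%, roughly 0.6 to 1.2 within-person SEs at a CV of 22%. The confounding follows from the design alone; the size rests wholly on the assumed shift. The change should be made because it is easy before the first session and cannot be recovered in analysis afterwards.

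**What to change.** In section 7.4, replace the fixed order with a randomised, balanced order for the healthy volunteers, and state whether there are one or two reference sessions.

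- One reference session: 5 volunteers reference-first, 5 bean-first.
- Two reference sessions: bean product first, second or third in 3, 4 and 3 volunteers.
- State whether GI and FII share sessions. Section 7.1 matches portions on carbohydrate and section 7.2 on energy. If the sessions are separate, balance the order within each index's own set.
- Optional sensitivity analysis: log iAUC with subject, food and visit terms, listing any session with zero iAUC, which cannot enter. Do not report indices by visit position; 3 to 5 people per position is uninformative.
- Apply the same to the T2DM patients only if they have a reference session.

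Cost: a short random list drawn up before the first session, with no added visits or assays and almost no loss of precision. Both foods must be ready on each study day. Because section 7.1 limits the reference solution to 72 hours and visits are a week apart, group days would mean one more batch of it. Balancing also relies on there being no carry-over across the one-week gap.
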